Setting: The POSH Clinic is an interdisciplinary collaboration between surgery, anesthesiology, geriatrics, nursing, and physical therapy to provide perioperative surgical care for high-risk Veterans at the Durham VAMC. The clinic opens with a conference to review patients to be seen that day. The surgery chief resident presents and the team covers technical issues with the surgery and selection of anesthesia, as well as covering a list of specific care points. The POSH clinic estimates 200 – 400 patients enrolled annually.

VAPOSH Veterans who are malnourished or at risk of being malnourished will be randomly assigned on a 1:1 ratio by computer-generated random numbers to either an education (nutritional counseling) control (PoshControl) arm or high-protein perihabilitation (PeriHab) arm. All will receive nutrition education. Participants in the PeriHab arm will also be provided with high quality protein supplements that will bring their protein intakes to at least 30 grams for each of the 3 meals per day.

Study Arms:

- PoshControl; n = 42: During their VAPOSH clinic visit, participants will be provided nutrition counseling and prescribed to consume protein at 1.0 g/kg of body weight in the form of educational handouts explained by a Registered Dietitian. Participants will also be instructed to consume 1 oral nutrition supplement per day two weeks before surgery.
- PeriHab; n = 42: PeriHab will be provided nutrition counseling and prescribed to consume protein at 1.6 g/kg of body weight) as well as provided 30 g of high quality protein to some 3 times per day for 2 weeks before and 4 weeks after surgery.

Measurements:

After the participant has been consented and HIPAA Authorization forms have been signed, a Registered Dietitian will administer the NRS-2002 screening tool, the PG-SGA, and nutrition focused physical exam. A patient screening “nourished” on the NRS-2002, PG-SGA, and nutrition focused physical exam will not be included in the study. For study candidates who are malnourished or at nutritional risk we will then proceed with baseline assessments (described below). Upon the completion of all baseline assessments, the participant will be randomized to PeriHab or PoshControl. The following variables will be blocked in this order: 1) surgery type and 2) American Society of Anesthesiology (ASA) Physical Status Classification System (≥ 3 versus < 3). An equal number of participants will be randomized across the two arms.

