| 
 Referred to VAPOSH (at increased risk for post-operative complications) Abdominal surgery (upper GI, colorectal, hepatobiliary, pancreatic, intra-abdominal, | 
 Living in skilled nursing facility Having any surgery other than abdominal surgery A score of <21 (high school edu.) or <20 (less than high school edu.) on the Montreal Cognitive Assessment (MoCA) or Saint Louis |

| | |
|--|--|
| 
bladder, VATS/lobectomy and abdominal aortic aneurysm)
 
 • Age ≥ 60 years • Malnourished or at nutritional risk (PG-SGA and Nutrition Focused Physical Exam) • English speaking | 
University Mental Status (SLUMS) and inability to perform 1 or more activities of daily living (ADL).
 
 • A diagnosis of Galactosemia, a rare genetic metabolic disorder that affects an individual's ability to metabolize the sugar galactose properly. |
|--|--|

Only participants scheduled for a POSH clinic visit will be eligible for study participation. [name] or study staff will meet with the coordinator of the POSH clinic, weekly to identify eligible patients. We will screen and consent individuals until we meet the desired sample size of 84 subjects. The POSH clinic has over 300 visits annually.

To protect vulnerable populations or those subjects who may be susceptible to coercion or undue influence against, any Veteran who is approached by staff will be told that their participation is voluntary, and they may choose not to answer any questions that they find too sensitive. Also, Veterans will be told that their participation will not affect their care at the VA. The study staff member will explain the study in detail. No study procedures will begin until formal, written informed consent has been obtained.

Subject Recruitment

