Aim 1.2 Analysis Plan: This design is a two-armed clinical trial, with replicate measures at three time points: baseline, two, and six weeks. Since subjects are randomized to either PeriHab or PoshControl arm, and the groups are presumed equal at baseline, the analysis is straightforward. Following the Good Clinical Practice Guidelines for the analysis of a clinical trial, we will employ mixed models,⁴³ analyze under an Intent to Treat (ITT) criteria, and control for baseline and assess the impact of Time, Treatment Group and the interaction of these variables on the outcomes. Relative to the usual repeated measures designs, mixed models have several advantages: 1) missing values present no particular difficulties in estimation and the estimates are unbiased as long as the set of variables leading to MAR are estimated, 2) the usual assumption of conditional independence (compound symmetry) used in standard repeated measures need not be made, and 3) the actual times of measurement need not be equivalent across subjects. Controlling for the individual baseline values for the particular outcomes, the trajectories over time and differences in those trajectories will be assessed. Following the statistical principles section from the International Conference on Harmonization, we will select covariates (e.g., age, race, number of comorbidities) for the primary models a priori, but we also will conduct auxiliary sensitivity analyses that evaluate whether potential group imbalances bias the treatment effect estimate. These analyses will be performed using conventional testing for confounding.

For any particular outcome, the general form of the model will be:

$$Y_{it} = \beta_0 + \beta_1(\text{group}) + \beta_2(\text{time}_t) + \beta_3(\text{group} * \text{time}_t) + \beta_4(\text{covariates}) + \varepsilon_{it}$$

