The results of these analyses will provide invaluable information regarding the process and functional forms and, potentially, the causal pathways of the intervention process. For example, one important analysis will enter 'level of compliance to the intervention' into the analysis, allowing for a 'per protocol' analysis of the results.

Power Estimate: Estimate effect sizes for the physical function between-group comparisons and the power available to detect effect with two-tailed tests are provided below for the total N= 80. The objective of this pilot study is to perform preliminary evaluation of a nutrition perihabilitation program in malnourished Veterans, in preparation for a larger grant submission. This pilot work will allow us to conduct sample size, effect sizes, and power analyses for a larger clinical trial. To date, no randomized controlled nutrition perihabilitation study has been conducted in malnourished Veterans. As such, we turned to the literature. Gillis et al.,⁴⁶ reported that older adults undergoing colorectal resectioning surgery who were given nutrition supplementation 3 weeks before surgery improved by 23.7 meters on the 6 minute walk test while the arm given nutrition supplement following the surgery declined by -21.3 meters. The pooled standard deviation of these changes was 67.75. Thus, a standard difference of $0.66 = (23.7 - (-21.3))/67.75$ was observed. Differences of this magnitude have been labeled as 'medium' in the statistical power literature (70). Assuming a standard deviation in the change scores of 67.75, n=40 per group, power=80% and alpha=0.05 (two-tailed), we are powered to detect a difference in changes scores of a standardized magnitude of 0.634, in line with the results of Gillis et al.⁴⁶

References

2. Morley J. Decreased food intake with aging. *J Gerontol Med Sci* 2001;56:81-88.

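### Testing for confounding is the wrong check on chance imbalance in a randomised comparison; replace it with one adjusted model fixed in advance and reported whatever the imbalance

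*Combined protocol and SAP*

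**What the plan says.** The Aim 1.2 Analysis Plan (combined protocol and SAP) starts from randomisation and says that "the groups are presumed equal at baseline". For the primary analysis it states that "we will select covariates (e.g., age, race, number of comorbidities) for the primary models a priori". The same sentence adds "auxiliary sensitivity analyses that evaluate whether potential group imbalances bias the treatment effect estimate", and the next gives the method: "These analyses will be performed using conventional testing for confounding".

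Nothing further is specified: no test, threshold, list of variables, or consequence if confounding is declared.

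Two design facts matter here. Under Setting, participants are "randomly assigned on a 1:1 ratio by computer-generated random numbers". Under Measurements, "The following variables will be blocked in this order: 1) surgery type and 2) American Society of Anesthesiology (ASA) Physical Status Classification System". Neither blocking factor is among the example covariates in the analysis plan.

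**The concern.** Testing for confounding is a tool for observational data, where group membership may depend on patient characteristics. In this trial a computer-generated sequence determines group membership. Among all randomised participants, any baseline difference is therefore a chance difference. A test on it can only confirm that chance produced a difference; it cannot show that allocation biased the comparison.

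The second problem is selection. On either usual meaning of the phrase (significance tests of baseline differences, or screening covariates by how far they move the estimate), the covariates in the sensitivity model are those that happened to be imbalanced in this sample. That sits badly beside a commitment to choose covariates in advance.

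Aim 1.2 exists to supply an effect size for a later, larger trial. A statement that this effect is confounded, or an alternative adjusted figure built from covariates picked by chance, could be carried into that planning.

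**Working it through.** **Inputs from the documents.** Allocation is 1:1. There are 84 participants, 42 per arm (Study Arms; Selection of Subjects: "We will screen and consent individuals until we meet the desired sample size of 84 subjects"). The Power Estimate uses fewer: "the power available to detect effect with two-tailed tests are provided below for the total N= 80", or 40 per arm. Its detectable standardised effect is 0.634 at 80% power and two-sided alpha 0.05. Three covariates are named as examples.

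**Assumed, because the documents are silent.** The decision rule, its threshold, the number of covariates screened, and their correlation r with the outcome. Covariates are taken as independent, the effect is on the change-score SD scale, and there is no dropout.

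**1. The plan's own figure.** The cited difference is (23.7 + 21.3)/67.75 = 0.664, given as 0.66. A two-sample t-test with 40 per arm (noncentral t, 78 df) has 80% power at 0.6343. The stated 0.634 reproduces. It comes from a six-minute walk study and is used here only as the plan's reference effect.

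**2. If the rule is a significance test on each baseline covariate.** With k independent tests at level α and sound randomisation, the chance of at least one flag is 1 − (1 − α)^k.

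| Covariates | α = 0.05 | α = 0.10 |
|---|---|---|
| 3 | 1 − 0.95³ = 14% | 1 − 0.90³ = 27% |
| 10 | 1 − 0.95¹⁰ = 40% | 1 − 0.90¹⁰ = 65% |

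Sample size does not enter this formula.

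**3. If the rule is a 10% change in the estimate, one covariate, no baseline adjustment.** Adjustment moves the estimate by roughly r times the chance imbalance. With 42 per arm the imbalance has SD √(2/42) = 0.218 covariate SDs. The flag threshold at the plan's effect is 0.1 × 0.634 = 0.0634.

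| r | SD of shift | Threshold / SD | Normal approximation | Simulated, effect 0.634 | Simulated, effect 0.4 |
|---|---|---|---|---|---|
| 0.2 | 0.0436 | 1.45 | 15% | 20% | 38% |
| 0.3 | 0.0655 | 0.97 | 33% | 33% | 51% |
| 0.4 | 0.0873 | 0.73 | 47% | 46% | 63% |

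Simulation exceeds the approximation at r = 0.2 because the slope and the effect are themselves estimated. At effect 0.4 the unadjusted and adjusted estimates both average about 0.40, so neither is biased and the flags do not indicate bias.

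This rule does depend on trial size. With three covariates at r = 0.3 and effect 0.634, at least one is flagged in 67% of trials with 40 per arm and 13% with 200 per arm. It also depends on the effect: at a true effect of zero, 40 per arm and r = 0.2, one covariate is flagged in 63% of trials, because the percentage change is taken on a near-zero estimate.

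**4. The same rule with the baseline outcome already in the model.** The plan says it will control for each outcome's baseline value. If baseline and outcome correlate 0.6, and covariate and baseline 0.4, the rates for r = 0.2, 0.3, 0.4 are about 4%, 5%, 15% at effect 0.634 and 12%, 15%, 32% at effect 0.4. Across a wider set of assumed correlations the range is about 3% to 40%. The reduction comes from overlap between the covariate and the baseline outcome. A covariate unrelated to baseline gains little from it.

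**The case against.** The strongest reply is that the plan never describes the procedure being criticised. It gives no p-value rule or change-in-estimate threshold, so any single false-flag rate is supplied by the critic. That stands, and every rate above is conditional. A reader might infer that a large share of sound trials of this size would be flagged. The documents do not support that as a general statement: tests at 0.05 on the three named covariates give 14% whatever the size, the stated baseline adjustment lowers the change-in-estimate rates where the covariate overlaps with baseline, and blocking would lower them for surgery type and ASA class.

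A reader might also infer that the primary result is exposed to data-driven covariate choice. It is not. Primary covariates are to be chosen in advance, these analyses are labelled auxiliary, and no text lets a flag replace or reinterpret the primary estimate. Nor does the plan mention p-values in baseline tables, so there is nothing to correct there.

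Two further points have force. First, chance imbalance in a prognostic covariate does shift the estimate in the one trial at hand, so an adjusted result is worth having. This supports adjustment, not a test that decides whether to adjust. Second, Withdrawal of Participants removes people after enrolment for no surgery, emergency surgery, or refusing the supplement, and supplement burden differs by arm. Imbalance among those with follow-up may therefore not be chance. That is a fair worry, but it is a missing-data question, the analysis plan does not name it as the target, and a confounding test would not resolve it.

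**Conclusion.** The point holds as a minor one about method. A confounding test cannot answer whether random allocation biased the comparison, and it makes the sensitivity model depend on observed imbalance. That conclusion needs only the randomised design and the plan's own sentence.

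The size does rest on assumptions. Significance tests at 0.05 give a false flag in 14% of sound trials with three independent covariates and 40% with ten. A 10% change-in-estimate rule on one covariate with r of 0.2 to 0.4, 42 per arm and effect 0.634 gives about 20% to 46% without baseline adjustment, and about 3% to 40% with it. The consequence is confined to how robust the pilot's effect size is said to be.

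**What to change.** Delete the sentence on testing for confounding. In its place, specify one sensitivity model: the primary model plus a closed list of baseline covariates chosen for expected prognostic strength. The list should include surgery type (in the categories used at randomisation) and ASA class (3 or above versus below 3), unless the primary model already contains them. Keep it short, given 84 participants. State that its estimate and confidence interval will appear beside the primary result whatever imbalance is observed, with no test deciding whether to show it. For the primary model to be fixed too, its example covariates need to become a final list.

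Handle imbalance arising from withdrawal after randomisation separately, under missing data.

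The cost is about two sentences of SAP text. It needs no new data and less analysis than the present wording implies.

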Where i is an indicator of person, and time is defined as $t=1, 2$ (measuring week 2 or 6), and the β 's are regression coefficients connecting the predictors to the outcome. For brevity, we list β_4 as a vector of K regression coefficients linking the K covariates to the outcome. As defined, the overall test of the intervention effect will be the joint effect of group and group*time on 2 df (β_1 and β_2) assessing an overall effect of group, and if this group effect is constant over time. If significant, follow-up tests will assess where group differences lie. In particular, we note that if the time by group interaction is rejected, we will test if the groups differ at the end of 6 weeks (a test of effect at the completion of the intervention).

We will carefully examine model assumptions, including the distribution of model residuals, additively, linearity, and influential observations, and will, if necessary, re-parameterize the models or transform the outcomes accordingly.

We note that we have listed numerous measures to be analyzed as outcomes, but have listed only 2 domains of outcomes as primary (physical function and a biological index of nutrition status and inflammation). We will not adjust for Type-I error rate for these primary outcomes. Rather, we will warn the reader of the multiple outcomes tested and the chance for a Type-I error.

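### Aim 1.2: the overall intervention test carries a wrong subscript (minor: β2 should read β3), and the randomization blocking factors should be named as covariates in the primary models (near-free improvement)

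*Combined protocol and SAP*

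**What the plan says.** All references are to the combined protocol and SAP.

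- **Model (Aim 1.2 Analysis Plan).** β1 multiplies group. The next two terms are "\beta_2(\text{time}_t) + \beta_3(\text{group} * \text{time}_t"), so β2 is time and β3 is the interaction. β4 is the vector of covariate coefficients. For time coding, "time is defined as $t=1, 2$ (measuring week 2 or 6").
- **Overall test (same section).** It is the "joint effect of group and group*time on 2 df (β_1 and β_2) assessing an overall effect of group". The sentence then gives a second purpose for the test, namely constancy of that effect: "and if this group effect is constant over time". The test is defined nowhere else.
- **Follow-up (same section).** "if the time by group interaction is rejected, we will test if the groups differ at the end of 6 weeks".
- **Randomization (Measurements).** "The following variables will be blocked in this order: 1) surgery type and 2) American Society of Anesthesiology (ASA"), with ASA class split at ≥3 versus <3.
- **Covariates (Aim 1.2 Analysis Plan).** The analysis controls for the baseline value of the outcome, and "we will select covariates (e.g., age, race, number of comorbidities) for the primary models a priori". Auxiliary sensitivity analyses then look at group imbalance by conventional tests for confounding, with no rule given.

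**The concern.** **Label.** The sentence that defines the overall test gives one pair of terms in words (group and group-by-time) and another in symbols (group and time). Both pairs have 2 df, so a degrees-of-freedom check would not reveal the mismatch. If the symbols were coded as printed, change between the two follow-up visits that both arms share would count towards an intervention effect.

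**Covariates.** Blocking on a prognostic factor makes the arms more alike than simple randomization would. A model that omits the factor does not credit that gain: its standard error is too large, the test rejects too seldom under the null, and the interval is wider than it need be. Interval width matters here because Aim 1.2 exists to estimate an effect size for a larger trial.

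**Working it through.** **1. The plan's own figure.** Inputs from the Power Estimate: 40 per group, two-sided alpha 0.05, power 80%. For a two-sample t test with 78 df and d = 0.634, the noncentrality is 0.634 × √(40/2) = 2.835 and the critical value is 1.991. Power is 0.800, and solving for 80% power gives d = 0.6343. The stated 0.634 is reproduced. It comes from a two-group comparison of change scores and does not depend on the β labels.

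**2. Label against model.**

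| Source in the Aim 1.2 plan | Terms | Coefficients | df |
|---|---|---|---|
| Test in words | group, group × time | β1, β3 | 1 + 1 = 2 |
| Test in symbols | group, time | β1, β2 | 1 + 1 = 2 |
| Stated purpose (constancy of the group effect) | group × time | β3 | – |
| Follow-up rule | group × time | β3 | – |

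Group has 1 df (two arms), and time and the interaction have 1 df each (two follow-up visits). β4 is taken by the covariates, so no reading of the equation makes β2 the interaction. Only (β1, β3) fits the words, the purpose and the follow-up rule.

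**3. Blocking factors left out of the model.** Let R² be the share of residual variance that surgery type and ASA class explain after baseline and the other covariates. The documents give no value, so 2–20% is assumed. Because blocking balances these factors, the true variance of the group difference is (1 − R²) times what the unadjusted model estimates. In large samples:

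- true type I error = 2[1 − Φ(1.96/√(1 − R²))]
- ratio of interval widths, without to with the factors = 1/√(1 − R²)

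| Assumed R² | 1.96/√(1 − R²) | Type I error | Width ratio |
|---|---|---|---|
| 0.02 | 1.980 | 4.8% | 1.010 |
| 0.05 | 2.011 | 4.4% | 1.026 |
| 0.10 | 2.066 | 3.9% | 1.054 |
| 0.20 | 2.191 | 2.8% | 1.118 |

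**4. Cost of including them.** With surgery type collapsed to four groups (assumed), the cost is 3 df plus 1 df for ASA class, so 4 df. Taking 77 error df as the starting point for N = 80, the two-sided 5% t critical value goes from 1.9913 (77 df) to 1.9930 (73 df). The ratio is 1.0009, an increase of about 0.09%.

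**The case against.** **The label is harmless.** The same sentence names the right terms, the stated purpose and the follow-up rule agree with it, and earlier in the section the plan undertakes to "assess the impact of Time, Treatment Group and the interaction of these variables on the outcomes". An analyst who follows the words runs the right test, and no sample size, power or alpha changes. The text was also read from PDF, so a misread digit cannot be excluded from the text alone, although nothing points to one. This stands, and it is why the item is minor.

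A reader might go further and infer that the trial will report shared change across surgery as a treatment effect. Coded literally, with no treatment effect, 40 per arm, group coded 0/1 and an assumed shared change of 0.3 SD between visits, the (β1, β2) test would reject in 55–74% of trials for an assumed within-person correlation of 0.5–0.7. The (β1, β3) test would reject in 5%. The shared change, the correlation and the group coding are all absent from the documents, and the result moves with each. The documents do not support that reading: their words prescribe the correct test. Such figures illustrate what the printed symbols mean and should not set the severity.

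**The covariate list is open.** It is given only by example, and nothing excludes surgery type or ASA class. A reader might infer that the plan omits its blocking factors or contradicts its randomization; it does neither. The gain also rests on an assumed R². Baseline adjustment and comorbidity count may already absorb part of what ASA class carries, so the low end of the range may apply. Both points stand, and they make this an improvement rather than an error.

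**The imbalance analyses might bring the factors in.** That depends on a rule the plan does not state. A test of imbalance will seldom flag factors that were balanced by design, while a change-in-estimate rule may flag them erratically when the effect is near zero. Neither replaces naming them in advance.

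**Conclusion.** Two items, of different kinds.

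1. **Wrong as written, minor.** The label (β1 and β2) contradicts the model equation and the words beside it. It should be corrected because this is the sole definition of the overall test and the df count hides the slip. This conclusion rests on the document alone.

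2. **Near-free improvement.** The primary models should name the two blocking factors. Leaving them out makes the test conservative; it does not produce false positive claims. The size rests on the assumed residual R² and the large-sample formulas. At 2% the loss is negligible; at 20% it is a modest but real loss of precision.

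**What to change.** 1. In the sentence defining the overall test, replace (β1 and β2) with (β1 and β3). A sentence stating how group is coded would help readers of the output: with group 0/1 and the plan's t = 1, 2, the week-6 difference is β1 + 2β3. Cost: one character and, if wanted, one sentence.

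2. In the covariate sentence, name ASA class (≥3 versus <3) and surgery type as fixed covariates in the primary models, and list in advance how small surgery categories will be collapsed. Both variables are already recorded for randomization. Cost: SAP wording and 4 df if surgery type is collapsed to four groups.

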Introduction. Malnutrition is recognized as a major concern by healthcare providers, as well as by patients, families, and caregivers. In a very recent survey, 28% of 1,035 patients, families and caregivers reported that malnutrition was a very significant problem, while 55% reported it was a somewhat significant problem in older adults 65 and older.²⁶ This response aligns with reports that up to 65% of older adults admitted to the hospital are malnourished (National Resource Center on Nutrition, Physical Activity, and Aging, 2015). Thus, it is essential to establish systematic malnutrition screening in the clinical setting and to develop intervention models and standards of nutritional care. The objective of this aim is to investigate the feasibility, fidelity and acceptability of a nutrition intervention protocol providing higher protein intakes before and after surgery in malnourished Veterans. To achieve the objective of this aim, we will test our working hypotheses that recruitment in clinic will have a high yield and that intervention fidelity (adherence, retention) and acceptability (attrition, patient satisfaction) will be predominantly satisfactory. The rationale for this aim is that successful completion of the proposed research will provide necessary knowledge to begin to identify feasible and acceptable interventions for community-dwelling Veterans who are preparing for surgical procedures. When the proposed studies for Aim 1.1 have been completed, it is our expectation that $\geq 75\%$ of patients approached for recruitment will agree to participate, $\geq 75\%$ of the time patients will adhere to the intervention, $\geq 80\%$ of the participants will remain in the study, and that $\geq 80\%$ of participants will find the intervention to be acceptable. Such findings would be of considerable importance, providing a patient-centered viewpoint that will inform the development of nutrition interventions that meet the standards and needs of high-risk Veteran Populations.

Specific Aim 1.2 – *To determine the effect size for planned future studies of enhanced protein supplementation in malnourished Veterans, with physical function as the primary outcome of interest. Of secondary interest are: biomarkers of inflammation (albumin, hsCRP, TNF- α , IL-6), dietary intake, hospital readmission, discharge location, length of skilled care, and ED admission, and physical activity.*

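### The 80% power is stated for a single change-score comparison, but the planned overall test has 2 df, and the only week-6 comparison described sits behind it and an ambiguous interaction condition

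*Combined protocol and SAP*

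**What the plan says.** The Power Estimate section works from an external 6-minute walk result. It sets out its inputs as "Assuming a standard deviation in the change scores of 67.75, n=40 per group", with 80% power and a two-sided 5% level, and concludes that "we are powered to detect a difference in changes scores of a standardized magnitude of 0.634". It does not say which visit the change runs to, and it mentions neither a joint test, nor an interaction, nor baseline adjustment.

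The Aim 1.2 Analysis Plan fits a mixed model to weeks 2 and 6, adjusted for baseline. There, "the overall test of the intervention effect will be the joint effect of group and group*time on 2 df". Follow-up tests come only if that test is significant. On the end-of-intervention comparison the plan adds that "if the time by group interaction is rejected, we will test if the groups differ at the end of 6 weeks". This is the only week-6 comparison it describes.

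Specific Aim 1.2 gives the purpose: "To determine the effect size for planned future studies of enhanced protein supplementation in malnourished Veterans", with physical function as the primary outcome. No section says which visit, which SD or what confidence interval will define that effect size.

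**The concern.** The power statement and the analysis rule describe different procedures. A power figure for a 1-df comparison does not carry over to a 2-df test, and still less to a comparison reached only after other tests.

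The interaction condition matters most. If 'rejected' means that the null hypothesis of no interaction is rejected, a benefit of equal size at both visits would rarely be tested at week 6, because there is no interaction to find. If it means that the interaction term is dropped, a benefit that appears only after surgery would rarely be tested. Week 2 is the day of surgery and week 6 is four weeks later, so the pattern cannot be taken as known.

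At stake are the relevance of the quoted 80% and the soundness of the number this pilot is meant to hand to the next trial.

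**Working it through.** **1. The plan's own figure.** Inputs from the Power Estimate: n = 40 per group, power 80%, two-sided alpha 0.05. For a two-sample t-test on 78 df with noncentrality d·√(40/2), solving for 80% gives d = 0.6343, and power at d = 0.634 is 79.96%. The stated figure is reproduced, as a 1-df comparison. At the 42 per arm in the Design section (84 completers), power at 0.634 is 81.9%.

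**2. Assumptions for the planned tests.** The documents give neither the week-2/week-6 correlation ρ nor the week-2 effect d2. I took ρ = 0.3, 0.5 and 0.7; d2 = 0 (late only), half of d6, or equal to d6 (constant); d6 = 0.634; 40 per arm; and first, no gain from baseline adjustment.

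**3. The 2-df joint test.** It is an F test on 2 and 77 df with noncentrality λ = (n/2)(d2² − 2ρ·d2·d6 + d6²)/(1 − ρ²).
- Constant effect, ρ = 0.5: λ = 20 × 0.402/0.75 = 10.72, power 83%.
- If d2 = ρ·d6, so that week 2 adds no information: λ = 20 × 0.634² = 8.04, power 70%. Reaching 80% would then need d6 = 0.708.
- Over the whole grid: 70-95%.

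**4. The interaction test.** Its noncentrality is (d6 − d2)/√(2(1 − ρ) × 2/n).
- Constant effect: this is 0, so the test rejects 5% of the time.
- Half at week 2, ρ = 0.5: 0.317/√0.05 = 1.418, power 29%.

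**5. Chance of reaching and winning the week-6 test.** Simulated with 200,000 trials per setting; ranges are over ρ = 0.3 to 0.7.

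| Effect pattern | Joint test alone | Week 6, ungated | Joint, then week 6 | Joint, significant interaction, week 6 | Joint, interaction dropped, week 6 |
|---|---|---|---|---|---|
| Constant | 77-88% | 80% | 73-77% | 3-4% | 69-74% |
| Half at week 2 | 70-74% | 80% | 69-71% | 21-39% | 32-49% |
| Late only | 74-95% | 80% | 71-79% | 58-77% | 2-14% |

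**6. Baseline adjustment.** Assume it removes 25% of the variance (baseline-outcome correlation 0.5, not in the documents). The effective effect is 0.634/√0.75 = 0.732.
- Ungated week-6 test: 90%.
- Joint, then week 6: 82-90%.
- Joint, significant interaction, week 6: 4% (constant), 27-52% (half), 73-89% (late only).

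**7. The estimate.** With time coded 1 and 2, the model's group difference is β1 + β3 at week 2 and β1 + 2β3 at week 6, available whatever the p values. The 95% CI half-width for a standardised difference d, 1.96·√(2/40 + d²/160), is 0.44 at d = 0 and 0.45 at d = 0.634. If the week-6 estimate were kept only when the gates and the week-6 test were passed, a true 0.634 would average 0.71-0.75 (joint test and week 6) or 0.71-0.86 (significant interaction as well): about 13% to 35% too large.

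**The case against.** The strongest reply is that the gates govern tests, not estimates. Aim 1.2 asks for an effect size without any significance condition, and the mixed model supplies the week-6 difference regardless. This stands. A reader might infer that the effect size is reported only after significance; the documents do not say so. The inflation in step 7 is a risk if gated results alone are carried forward, not a stated rule.

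A reader might also infer that the planned analysis cannot deliver 80% power. That is too strong. The 2-df test is a legitimate overall test for an intervention acting before and after surgery, and it exceeds 80% for some patterns. With the assumed baseline adjustment, the joint-then-week-6 path does too.

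The plan introduces the interaction sentence as a particular case, so other follow-up tests are not excluded. On the single-gate reading the shortfall is only about 1 to 11 points. Nor does the Power Estimate name week 6 as its visit.

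What remains is that no power is given for the test the plan calls overall, that the one week-6 rule it does write down works badly under either reading for some plausible pattern, and that no estimate is named. Baseline adjustment does not rescue the interaction-gated path for a constant benefit: 4% instead of 3-4%.

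**Conclusion.** The point holds as a mismatch and an omission. The 0.634 figure is right for a 1-df comparison, but it is not the power of the 2-df test (about 70-95% here) or of the gated week-6 test. Taken literally, with a significant interaction required, the rule would reach and win the week-6 test about 3-4% of the time when a 0.634 SD benefit is present equally at both visits, against 80% for the same test run directly. With the interaction dropped instead, the weak case is a late-only benefit, at 2-14%.

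These sizes rest on assumed correlations, assumed week-2 effects, 40 per arm and no baseline gain. The direction for a constant effect under the literal reading does not depend on the correlation, since the interaction test then rejects only at its 5% level. The documents do not make the Aim 1.2 effect size conditional on significance; they leave it undefined, and that is the gap to close.

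**What to change.** - Name the baseline-adjusted group difference in SPPB at week 6 as the Aim 1.2 estimate. Estimate and test it whatever the joint and interaction tests show.
- Report it with its SD, as a standardised difference, and with a 95% CI (expect a half-width of about 0.44 SD). Quote the limits wherever it is used to size the next trial.
- Attach the 80% power statement to that contrast and name the visit.
- Keep the 2-df and interaction tests as supporting. Say what 'rejected' means, and correct the coefficients named for the joint test: the text lists β1 and β2, but the interaction is β3 in the model.
- If the 2-df test stays primary, restate its power under declared assumptions: about 70% at 0.634 when week 2 adds no information.

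The biological-index domain can stay as it is. The cost is analysis-plan wording, with no change to data collection or sample size. The one real loss is that an SPPB effect present only at week 2 would no longer be part of the powered test.
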